9.4.1 Archiving of study documents

The investigator follows the principles outlined in the CSA.

9.5 Study timetable and end of study

The end of the study is defined as ‘the last visit of the last healthy volunteer undergoing the study’.

The study is expected to start in Q1 2014 and to end by Q2 2014.

The study may be terminated at the study center if the study procedures are not being performed according to GCP, or if recruitment is slow. AstraZeneca may also terminate the entire study prematurely if concerns for safety arise within this study or in any other study with selumetinib.

10. DATA MANAGEMENT

Data management will be performed by

A 21 Code of Federal Regulations part 11 compliant electronic data capture (EDC) system, the Phase I Clinical Trial System (PICTS) will be used for this study. Electronic CRFs will be produced by _____ for each healthy volunteer. The majority of study data collected will be either directly entered by _____ clinical research personnel or directly captured from devices onto the eCRF. Data will be available for AstraZeneca review via predefined reports extracted from the database at agreed intervals.

The eCRFs must be kept in order and up-to-date so that they reflect the latest observations on the enrolled healthy volunteers.

When direct data entry into the eCRF is inappropriate or impractical, data will be collected on paper source documents and subsequently transcribed, where necessary, into the eCRFs by the clinical research personnel of _____. All source documents will be retained by _____. Photocopies of completed source documents will be provided only if essential (ie, for regulatory purposes) at the request of the AstraZeneca.

Safety laboratory data are managed and stored within the LIMS system and only the date and time of sampling are recorded in the eCRF. Safety laboratory data will be integrated with the consolidated clinical data before database lock.

The ICF will be kept with a copy of the completed source documents in the appropriate file folder provided, or a note to indicate where the records can be located. All records should be kept in conformance to applicable national laws and regulations.

Validity and consistency of data will be checked by employing pre-programmed data validation rules that will be applied to the data extracted from the EDC system during the course of the study. The data management team will raise queries in the EDC system to resolve discrepancies. The principal investigator must verify that all data entries in the eCRFs are accurate and correct. After completion of the study and when all collected data is validated, the database will be locked. Final data will be extracted from the EDC and delivered to the AstraZeneca in form of SAS[®] datasets.

All eCRF entries, corrections, and alterations must be made by the principal investigator or other authorized study center personnel and only by individuals who have received training on the EDC system. The study center personnel may be allowed access to the system only after training is completed. Training must be documented and a log of all EDC users and their rights within the system be maintained.

Adverse events and medical history will be coded using the current Medical Dictionary for Regulatory Activities (MedDRA) vocabulary and concomitant medication will be coded using the AstraZeneca Drug Dictionary as appropriate.

The EDC system will keep track of all data entry, alterations, and query resolution in an audit trail. The audit trail will form an integral part of the database and will be archived alongside with the data.

11. EVALUATION AND CALCULATION OF VARIABLES

11.1 Calculation or derivation of safety variable(s)

11.1.1 Calculation of change-from-baseline

Change-from-baseline variables will be calculated for the safety variables listed below, as the post-treatment value minus the value at baseline. The baseline values will be as follows:

- Clinical laboratory tests: last measureable value taken prior to the first investigational product administration.
- Vital signs: last measureable value taken prior to the first investigational product administration.

- Paper ECG: last measureable value taken prior to the first investigational product administration.

If a healthy volunteer is missing the baseline collection, the previous non-missing evaluation will become the baseline value. If no baseline or prior-to-baseline evaluations exist, then the baseline value will be treated as missing and no change-from-baseline value will be calculated.

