1.3.4 Summary of adverse events with rifampicin

Rifampicin is an antibiotic used in combination with other antibiotics to treat active tuberculosis (generally 6 months treatment) or for the prevention of tuberculosis in susceptible close contacts or those who have become tuberculin positive (generally 3 months treatment). It is generally well tolerated although it stains body fluids (including urine and tears) orange and can discolor soft contact lenses. Rifampicin can cause transient increases in liver transaminases and occasionally, especially in those with pre-existing liver disease, more

serious liver toxicity can occur necessitating discontinuation of treatment. Other AEs on continuous treatment are less common, but include, nausea, vomiting, diarrhea, hypersensitivity reactions, skin rashes and thrombocytopenia.

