2.2 Secondary objectives

The secondary objectives of the study are:

- To investigate the PK of N-desmethyl selumetinib when selumetinib is administered with or without rifampicin.
- To determine the plasma concentration of rifampicin at 2 hours after administration during the rifampicin dosing period to monitor the exposure of the CYP3A4 inducer.
- To determine the 4 β -hydroxycholesterol to cholesterol concentration ratios as a marker of CYP3A4 induction by rifampicin.
- To further assess the safety and tolerability of selumetinib by the assessment of AEs, laboratory variables, and vital signs.

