3.1 Overall study design and flow chart

This clinical study is designed as a Phase I, open-label, fixed sequence, single-center study to investigate the effect of rifampicin (a known CYP3A4 inducer) on the PK, safety and tolerability of a single 75 mg oral dose of selumetinib in healthy male and female (of non-childbearing potential) volunteers. Approximately 24 healthy volunteers aged between 18 to 45 years (inclusive), will be enrolled in the study. Withdrawn healthy volunteers will not be replaced; however, additional volunteers may be included in the study until such a time as 20 evaluable volunteers have completed both treatments. Screening procedures will only be performed for healthy volunteers who provide written informed consent.

The study will consist of 3 visits. Visit 1 will be a screening visit and will take place within 28 days of Visit 2. Visit 2 will be the treatment visit and the healthy volunteers will be resident at the study center from Day -1 up to Day 15. Visit 3 will be the follow-up visit and will take place 7 to 10 days after discharge on Day 15, Visit 2.

Healthy volunteers will be assigned to the following treatment schedule:

- Treatment A: Healthy volunteers will receive a single oral dose of 75 mg (3 x 25 mg) selumetinib on Day 1. Safety assessments will be performed and blood samples collected for PK analysis until Day 4.
- Treatment B: Following completion of assessments for Treatment A on Day 4, volunteers will receive single, daily, oral doses of 600 mg (2 x 300 mg) rifampicin on Days 4 to 11.
- Treatment C: On Day 12, volunteers will receive 600 mg (2 x 300 mg) rifampicin with a single oral dose of 75 mg (3 x 25 mg) selumetinib administered at the same time. Once daily rifampicin administration will continue through Day 14.

Safety assessments will be performed and blood samples collected for PK analysis until Day 15.

The study flow chart is presented in [Figure 1](#)

Figure 1 Study flow chart

[figure not shown]

Table 2 Study plan

Days	Visit 1				Visit 2					Visit 3	
	Screening	Treatment A (selumetinib only)			Treatment B (rifampicin only)			Treatment C (selumetinib +rifampicin)		Discharge	Follow-up visit
	-28 to -2	-1	1	2 to 3	4	5 to 10	11	12	13 to 14	15	7 to 10 days after discharge
Informed consent	X										
Optional informed consent for genotyping ^j		X ^j									
Demographic data	X										
Medical/surgical history	X										
Hepatitis B, C, and HIV screen	X										

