- e 12-lead ECGs. Patients should be supine and resting for at least 10 minutes before the ECG recording. On the selumetinib administration days of each treatment period, ECGs will be recorded at pre-dose, 1.5 hours (t_{max}), 8 hours, and at follow-up.
- f Clinical laboratory tests consist of hematology, clinical chemistry and urinalysis assessments, full test screens will be performed at screening, Days -1, 4 (prior to rifampicin administration), 15, and at follow-up. Additional liver function tests will be performed every 3 days while on rifampicin (Days 6, 9 and 12).
- g Includes alcohol and cotinine .
- h Full physical examinations will be performed at screening and follow-up and brief physical examinations on Day -1 and at discharge, Day 15.
- i When PK and vital measurements are scheduled at the same time point, ECG and vital signs will precede PK, with the PK blood sample collected at the specified protocol scheduled time. Blood samples (2 mL) to measure selumetinib will be collected pre-dose, and at 0.5, 1, 1.5, 2, 2.5, 3, 4, 5, 6, 8, 12, 24, 36, 48 & 72 hours after selumetinib administration on Days 1 and 12.
- j Pharmacogenetics blood sampling is optional and will be done if the volunteer provides additional informed consent on Day -1 (Visit 2).
- k Blood samples (4 mL) to determine 4 β -hydroxycholesterol and cholesterol plasma concentrations prior to administration of rifampicin or selumetinib on Day 12 and before the rifampicin administration on Days 4 and 14.
- l Blood samples (2 mL) to measure plasma concentration of rifampicin at 2 hours after rifampicin administration on Days 7, 9, and 14.
- m Selumetinib 72 hour blood sample (2 mL) to collected prior to first administration of rifampicin.
- n Follicle-stimulating hormone will be tested at screening, only for post-menopausal females.

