12. STATISTICAL METHODS AND SAMPLE SIZE DETERMINATION

12.1 Description of analysis sets

12.1.1 Safety analysis set

All healthy volunteers who received at least 1 administration of investigational product (selumetinib or rifampicin) will be included in the safety population.

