Tabulations and listings of data for vital signs, ECGs, and clinical laboratory tests will be presented, as appropriate. Results from physical examinations will be presented separately in listings only. All continuous safety data will be summarized across all treatments for the absolute value at each scheduled assessment and for the corresponding change-from-baseline. For clinical laboratory tests, listings of values for each healthy volunteer will be presented with abnormal or out-of-range values flagged. Clinical laboratory data will be reported in Système International units in the CSR. Additional graphical presentations of the data eg, shift plots comparing baseline to on treatment values will be generated as appropriate to aid the interpretation of safety data.

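### A single pre-Day 1 baseline puts eight days of rifampicin into the Treatment C safety changes, and no hematology or non-liver chemistry value is scheduled that could separate them

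*Protocol*

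**What the plan says.** **Baseline.** Section 11.1.1 defines the laboratory baseline as "Clinical laboratory tests: last measureable value taken prior to the first investigational product administration" and applies the same rule to vital signs and ECG. It gives no treatment-specific baseline. Section 12.1.1 shows what counts as investigational product: "All healthy volunteers who received at least 1 administration of investigational product (selumetinib or rifampicin) will be included in the safety population". The first administration is therefore selumetinib on Day 1.

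**Sequence.** Section 3.1 fixes the order: selumetinib alone on Day 1 (A), rifampicin alone on Days 4 to 11 (B), both drugs on Day 12 (C). After that, "Once daily rifampicin administration will continue through Day 14".

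**Laboratory schedule.** Under Table 2, footnote f, "full test screens will be performed at screening, Days -1, 4 (prior to rifampicin administration), 15, and at follow-up". During rifampicin only liver tests are added: "Additional liver function tests will be performed every 3 days while on rifampicin (Days 6, 9 and 12"). Footnote f times the Day 4 draw relative to dosing but not the Day 12 draw.

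**Vital signs and ECG.** Table 2, footnotes c and e, schedule pre-dose readings on both selumetinib days.

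**Presentation.** Section 12.2.2 states: "All continuous safety data will be summarized across all treatments for the absolute value at each scheduled assessment and for the corresponding change-from-baseline". The synopsis says safety data are presented by treatment.

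**Purpose.** A secondary objective in Section 2.2 is "To further assess the safety and tolerability of selumetinib by the assessment of AEs, laboratory variables, and vital signs".

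**The concern.** With a fixed sequence and one drug-free baseline, each later treatment's change accumulates what came before it. By the second selumetinib dose the volunteers have taken rifampicin for 8 days, and the protocol expects rifampicin to have laboratory effects of its own. Section 1.3.4 says "Rifampicin can cause transient increases in liver transaminases" and also lists thrombocytopenia. Section 1.3.3 lists AST and ALT rises among the expected effects of selumetinib, so the two drugs overlap on the same analytes.

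A rifampicin shift that was complete before Day 12 would therefore appear in the Treatment C change column, and a reader comparing that column with Treatment A could attribute it to selumetinib. These summaries matter more than usual here. Under Section 6.3.3, a deterioration in a protocol-mandated assessment is itself reported as an adverse event only if it meets a seriousness criterion or leads to discontinuation. Asymptomatic laboratory shifts will reach the report mainly through the value and change tables.

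**Working it through.** The protocol states no figure for this point, so there is none to reproduce. The check sets the baseline rule against the schedule.

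**Step 1: rifampicin doses inside the Treatment C change.** Days 4 to 14 give 14 − 4 + 1 = 11 doses. Days 4 to 11 give 11 − 4 + 1 = 8, all before the Day 12 selumetinib dose. The other 3 (Days 12, 13 and 14) are given with or after it.

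**Step 2: what each change contains.** Let R1 be the rifampicin effect present just before the Day 12 dose, R2 the further rifampicin effect from Day 12 to Day 15, and S the selumetinib effect. Assume that effects add and that nothing remains on Day 12 from the first selumetinib dose.

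- Treatment C as written: Day 15 − Day −1 = R1 + R2 + S
- Treatment C from a Day 12 pre-dose value: Day 15 − Day 12 = R2 + S
- Treatment A: Day 4 before rifampicin − Day −1 = S

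S is given one symbol for simplicity. It need not be equal in A and C, since the study is run because rifampicin may lower selumetinib exposure.

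The numbers below are assumed, in arbitrary units, and are not from the protocol:

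| R1 | R2 | S | Day 15 − Day −1 | Day 15 − Day 12 | Day 4 − Day −1 |
|---|---|---|---|---|---|
| 0 | 0 | 5 | 5 | 5 | 5 |
| 10 | 0 | 5 | 15 | 5 | 5 |
| 10 | 3 | 5 | 18 | 8 | 5 |
| 10 | 3 | 0 | 13 | 3 | 0 |

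A Day 12 baseline removes R1. It isolates selumetinib only if R2 is zero. Treatment A contains no rifampicin under either rule.

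**Step 3: which variables have a Day 12 value (Table 2 and footnotes).**

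| Variable | Value between Day 4 pre-rifampicin and Day 15 | R1 separable? |
|---|---|---|
| Vital signs | Day 12 pre-dose | Yes |
| ECG | Day 12 pre-dose (none on Day 4) | Yes, for Treatment C |
| Liver tests | Days 6, 9 and 12; Day 12 not timed to dose | Only if Day 12 is pre-dose |
| Hematology, including platelets | None | No |
| Non-liver chemistry | None | No |

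Table 5 agrees with this reading: 5 full chemistry samples, 5 hematology samples and 3 liver-only samples.

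**Step 4: where Treatment A's laboratory result sits.** The Day 4 panel precedes rifampicin, so it is Treatment A's post-dose result. As the text reads, Table 2 places Day 4 under Treatment B and shows no post-dose laboratory draw under A. The assignment should be stated.

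**Step 5: blood volume.** Replacing the Day 12 liver-only sample with full chemistry and hematology changes the volume by 8.5 + 4 − 5 = 7.5 mL. The Table 5 total becomes 188.5 + 7.5 = 196.0 mL, against the 450 mL ceiling in Section 7.1.

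**The case against.** The best defense is that nothing is mislabeled. Treatment C is the combination, and change from a drug-free state is a legitimate description of a combination. Section 12.2.2 plans no comparison of A with C for safety; that contrast is specified for pharmacokinetic parameters only, and Section 12.2.3.1 says the study is not powered for formal hypothesis testing. Absolute values are summarized at each assessment and laboratory values are listed by volunteer. A rise in liver tests under rifampicin alone would therefore show on Days 6 and 9, before selumetinib is given again. Extra change columns can also be left to the statistical analysis plan, which was not available here.

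Most of this stands. It is why the pre-Day 1 baseline should be kept and why the point is minor. It does not cover hematology and non-liver chemistry: there the assessment-by-assessment display has nothing to show between Day 4 and Day 15, and an analysis plan cannot supply a sample that was not drawn.

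It is also fair to object that a Day 12 baseline does not isolate selumetinib, because rifampicin continues through Day 14. That is correct. The added column reduces the mixing and should be labeled accordingly.

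**Conclusion.** The point holds as a minor limit on interpretation. Every Treatment C change from the stated baseline carries the effect of 8 of the 11 rifampicin doses, given before the second selumetinib dose. This prior effect can be separated for vital signs and ECG, conditionally for liver tests, and not at all for hematology and non-liver chemistry on the written schedule.

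A reader might infer that the single baseline confounds the selumetinib safety objective as a whole. The protocol does not support that. Treatment A is measured against a drug-free baseline, its Day 4 panel is drawn before rifampicin, and its vital signs (to 24 hours) and ECGs (to 8 hours) are taken on selumetinib alone.

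The size of the rifampicin shift is unknown. The protocol gives no figure and describes the transaminase rises as transient, so no numerical bias is claimed. The algebra assumes additive effects and no carry-over from Day 1. The primary pharmacokinetic analysis is not affected.

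**What to change.** 1. **Section 11.1.1.** Keep the pre-Day 1 baseline. For Treatment C, add the change from the last value before the Day 12 dose. State that change from the pre-Day 1 baseline reflects both drugs, and that the Day 12-based change still includes rifampicin given on Days 12 to 14. No separate ECG baseline for Treatment B is proposed, because no Day 4 ECG is scheduled.
2. **Treatment assignment.** State that the Day 4 laboratory values taken before rifampicin are the post-dose values of Treatment A.
3. **Table 2, footnote f, and Table 5.** Time the existing Day 12 draw as pre-dose and make it a full chemistry and hematology panel.

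Items 1 and 2 cost wording and a little programming. Item 3 costs about 7.5 mL of blood per volunteer and some laboratory work. It needs no extra visit, and pre-dose blood is already drawn on Day 12 for selumetinib and 4β-hydroxycholesterol. Item 3 has to be settled before volunteers reach Day 12, because the missing values cannot be recovered later.

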11.1.2 Other significant adverse events

During the evaluation of the AE data, an AstraZeneca medically qualified expert will review the list of AEs that were not reported as SAEs and discontinuations of the investigational product due to an AE (DAE). Based on the expert's judgment, significant AEs of particular clinical importance may, after consultation with the AstraZeneca CPA Physician, be considered as other significant AEs (OAEs) and reported as such in the CSR. A similar review of laboratory/vital signs data will be performed for identification of OAEs.

Examples of these are marked hematological and other laboratory abnormalities, and certain events that lead to intervention (other than those already classified as serious), dose reduction or significant additional treatment.

11.2 Calculation or derivation of pharmacokinetic variables

11.2.1 Selumetinib and metabolites

Pharmacokinetic parameters will be determined by using standard non-compartmental methods with Phoenix[®] WinNonlin Professional Version 6.3 or higher) or SAS[®] Version 9.2 or higher). Standard Operation

Procedures and Work Instructions will be used as the default methodology, unless otherwise specified. Actual elapsed time from investigational product administration will be used for final PK parameter calculations. Pharmacokinetic parameter units will be consistent with the concentration units specified in the bioanalytical data.

The following PK parameters will be determined for plasma selumetinib and N-desmethyl selumetinib (and the amide metabolite, if deemed appropriate):

AUC Area under the plasma concentration-time curve from time zero to infinity, calculated by linear up/log down trapezoidal summation.

AUC_(0-t) Area under the plasma concentration-time from time zero to the time of the last quantifiable concentration, calculated by linear up/log down trapezoidal summation.

$AUC_{(0-12)}$	Area under the plasma concentration-time curve from time zero to 12 hours post-dose, calculated by linear up/log down trapezoidal summation.
C_{max}	Maximum concentration, obtained directly from the observed concentration versus time data.
t_{max}	Time to C_{max} .
CL/F	Apparent systemic plasma clearance (selumetinib only).
V_{ss}/F	Apparent volume at distribution equilibrium, mean residence time (MRT)*CL/F (selumetinib only).
V_z/F	Apparent volume at distribution (selumetinib only).
$t_{1/2}$	Terminal half-life.
λ_z	Terminal rate constant.
MR_{AUC}	AUC metabolite to parent ratio, N-desmethyl selumetinib AUC/selumetinib AUC.
$MR_{C_{max}}$	C_{max} metabolite to parent ratio, N-desmethyl selumetinib C_{max} /selumetinib C_{max} .
MRT	Mean residence time.

No dose adjustment is required for PK parameters which require selumetinib dose for calculation since the selumetinib dose being administered is based on the free base equivalent.

The following PK parameters for plasma selumetinib and N-desmethyl selumetinib (and the amide metabolite, if deemed appropriate) will be calculated for diagnostic purposes and listed, but will not be summarized:

$t_{1/2}$, Interval	The time interval of the log-linear regression to determine λ_z .
N	Number of data points included in the log-linear regression analysis used to determine λ_z (a minimum of 3 data points will be used for λ_z determination).
Rsq	Coefficient of determination for calculation of λ_z (λ_z and related

parameters will be reported only if R_{sq} is 0.800 or more).

$\%AUC_{ex}$

Percentage of AUC obtained by extrapolation (if the extrapolated area is greater than 20% then AUC for that specific profile will not be reported).

Additional parameters will be calculated, if deemed appropriate. Pharmacokinetic parameters will be computed and reported if the anomalous pre-dose concentration value is not greater than 5% of the C_{max} in the profile. If the anomalous pre-dose concentration value is greater than 5% of C_{max} in the profile, PK parameters for the profile will not be reported. If an anomalous concentration value is observed at the terminal phase and is judged as physiologically unreasonable, it will be excluded from computing parameter estimates.

